### 12.4 Annual progress report

The sponsor/investigator will submit a summary of the progress of the trial to the accredited METC once a year. Information will be provided on the date of inclusion of the first subject, numbers of subjects included and numbers of subjects that have completed the trial, serious adverse events/ serious adverse reactions, other problems, and amendments.

### 12.5 Temporary halt and (prematurely) end of study report

< The following text is applicable for studies without an investigational medicinal product.> The investigator/sponsor will notify the accredited METC of the end of the study within a period of 8 weeks. The end of the study is defined as the last patient's last visit.

The sponsor will notify the METC immediately of a temporary halt of the study, including the reason of such an action.

In case the study is ended prematurely, the sponsor will notify the accredited METC within 15 days, including the reasons for the premature termination.

Within one year after the end of the study, the investigator/sponsor will submit a final study report with the results of the study, including any publications/abstracts of the study, to the accredited METC.

<The following text is applicable for studies with an investigational medicinal product.> NA

The sponsor will notify the accredited METC and the competent authority of the end of the study within a period of 90 days. The end of the study is defined as the last patient's last visit.

The sponsor will notify the METC immediately of a temporary halt of the study, including the reason of such an action.

In case the study is ended prematurely, the sponsor will notify the accredited METC and the competent authority within 15 days, including the reasons for the premature termination.

Within one year after the end of the study, the investigator/sponsor will submit a final study report with the results of the study, including any publications/abstracts of the study, to the accredited METC and the Competent Authority.

# **12.6 Public disclosure and publication policy**

The Consortium Agreement following the CCMO statement regarding publication policy of the study results is subscribed.

8.9. Publication. Pursuant to the publication obligations set out in Section 5.12 of the TKI-Allowance Agreement, the Parties must ensure open access (free of charge, online access for any user) to all scientific publications relating to its Foreground under the Project subject to the conditions hereunder. In particular, the Parties shall ensure open access to the deposited publication at the latest: (i) on publication, if an electronic version is available for free via the publisher, or (ii) within six months of publication in any other case. A Party or Parties that intend to publish on the Foreground (jointly) owned by it shall provide the other Parties with the draft publication at least 30 (thirty) calendar days before publication. Any objection to the planned publication shall be made in writing to the Coordinator and the Party or Parties proposing the publication within 30 (thirty) calendar days upon receipt of the draft publication. If no objection is made within the time limit stated above, the Publication is permitted. For the avoidance of doubt, a Party shall not Publish Foreground or Background of another Party, even if such Foreground or Background is amalgamated with the Party's own Foreground, without the other Party's prior written approval.

8.10. Objections to Publication. An objection has to include a precise request for necessary modifications and shall be considered justified only, if:

a. the proposed publication includes another Party's Background, Foreground or other Confidential Information; or

b. the objecting Party's legitimate academic or commercial interests are harmed by the publication;

c. the proposed publication includes patentable Foreground and the objecting Party anticipates that it wishes to exercise the Option.

Upon receipt of an objection, the Parties involved shall discuss a solution in good faith. The objecting Party can request a publication delay of an additional period of 60 (sixty) calendar days (following the 30 day period referred to in clause 8.9). Upon expiration of the term, the publishing Party will be entitled to publish the proposed publication.

### **13. STRUCTURED RISK ANALYSIS**

NA

### 13.1 Potential issues of concern

a. Level of knowledge about mechanism of action NA

b. Previous exposure of human beings with the test product(s) and/or products with a similar biological mechanism NA

c. Can the primary or secondary mechanism be induced in animals and/or in *ex-vivo* human cell material? NA

d. Selectivity of the mechanism to target tissue in animals and/or human beings NA

e. Analysis of potential effect NA

f. Pharmacokinetic considerations NA

g. Study population NA

h. Interaction with other products NA

i. Predictability of effect NA

j. Can effects be managed? NA

# **APPENDIX 1:** Criteria for the diagnosis of DM according the ADA guidelines (7)

A1C $\geq$ 6.5%. The test should be performed in a laboratory using a method that is NGSP
certified and standardized to the DCCT
assay.*
OR
FPG ≥126 mg/dL (7.0 mmol/L). Fasting is
defined as no caloric intake for at least 8 h.*
OR
2-h plasma glucose ≥200 mg/dL (11.1 mmol/L) during an OGTT. The test should be performed as described by the WHO, using a glucose load containing the equivalent of 75 g anhydrous glucose dissolved in water.* OR
In a patient with classic symptoms of hyperglycemia or hyperglycemic crisis, a random plasma glucose ≥200 mg/dL (11.1 mmol/L).

\*In the absence of unequivocal hyperglycemia, result should be confirmed by repeat testing.

## APPENDIX 2: Categories for pre-DM according the ADA guidelines (7)

FPG 100 mg/dL (5.6 mmol/L) to 125 mg/dL
(6.9 mmol/L) (IFG)
OR
2-h plasma glucose in the 75-g OGTT 140 mg/dL $$
(7.8 mmol/L) to 199 mg/dL (11.0 mmol/L)
(IGT)
OR
A1C 5.7-6.4%

\*For all three tests, risk is continuous, extending below the lower limit of the range and becoming disproportionately greater at higher ends of the range.

# APPENDIX 3: The 10-year-risk chart of ASCVD (for patients without known ASCVD) (30)

	Vrouwen									Mannen											
SBD		Niet	-rook	ster			Re	ookst	ter		Leef-	Niet-roker					Roker				
180	35	38	41	43	44	47	50	>50	>50	>50	tijd	>50	>50	>50	>50	>50	>50	>50	>50	>50	>50
160	28	31	33	35	36	38	41	44	46	48		45	48	>50	>50	>50	>50	>50	>50	>50	>50
140	22	24	26	28	29	31	33	36	38	39	70	37	40	42	44	46	49	>50	>50	>50	>50
120	18	19	21	22	23	25	27	29	30	32		30	32	34	36	38	40	43	45	48	50
180	14	17	20	24	30	27	32	37	45	>50		25	30	36	44	>50	45	>50	>50	>50	>50
160	10	12	14	17	21	19	22	27	32	39		18	21	26	32	40	33	39	47	>50	>50
140	7	8	10	12	15	14	16	19	23	28	65	12	15	18	23	29	23	28	34	42	>50
120	5	6	7	9	11	10	11	14	17	20		9	11	13	16	21	17	20	24	30	38
180	10	12	15	18	23	20	23	28	34	42		22	26	32	40	50	40	48	>50	>50	>50
160	7	8	11	13	16	14	17	20	24	30		15	19	23	29	36	29	35	42	>50	>50
140	5	6	7	9	12	10	12	14	17	21	60	11	13	16	20	26	20	25	30	38	47
120	4	4	5	7	8	7	8	10	12	15		8	9	12	15	19	14	18	22	27	34
180	5	6	8	10	12	10	12	15	18	22		13	16	20	26	32	25	31	38	47	>50
160	4	4	5	7	9	7	8	10	13	16		10	12	15	18	23	18	22	27	34	43
140	3	3	4	5	6	5	6	7	9	11	55	7	8	10	13	17	13	16	19	24	31
120	2	2	3	3	4	4	4	5	6	8		5	6	7	9	12	9	11	14	17	22
180	2	3	4	5	6	5	6	7	9	11		8	10	12	15	20	15	18	23	28	36
160	2	3	3	3	4	3	4	5	6	8		6	7	9	11	14	11	13	16	20	26
140	1	1	2	2	3	2	3	3	4	6	50	4	5	6	8	10	7	9	12	15	19
120	1	1	1	2	2	2	2	2	3	4		3	3	4	6	7	5	7	8	10	13
180	1	1	1	1	1	1	1	1	2	2		3	3	4	6	7	5	6	8	10	13
160	<1	<1	1	1	1	1	1	1	1	2		2	2	3	4	5	4	4	6	7	9
140	<1	<1	<1	1	1	<1	<1	1	1	1	40	1	2	2	3	4	3	3	4	5	7
120	<1	<1	<1	<1	<1	<1	<1	1	1	1		1	1	2	2	3	2	2	3	4	5
	4	5	6	7	8	4	5	6	7	8		4	5	6	7	8	4	5	6	7	8
			Rati	o tot	aal eł	olest	erol/	HDL						Rati	o tot	aal ch	olest	erol/	HDL		

Tabel 1. Risicotabel: 10-jaarsrisico op ziekte of sterfte door HVZ voor patiënten zonder HVZ

< 10% risico op ziekte of sterfte door HVZ; leefstijladviezen indien daar aanleiding voor is, zelden medicamenteuze behandeling.

10% tot 20% risico op ziekte of sterfte door HVZ; leefstijladviezen, medicamenteuze behandeling alleen bij risicoverhogende factoren en SBD > 140 mmHg en/of LDL > 2,5 mmol/l.

≥ 20% risico op ziekte of sterfte door HVZ; leefstijladviezen, medicamenteuze behandeling als SBD > 140 mmHg en/of LDL > 2,5 mmol/l.

Het risico bij patiënten met DM of RA kan worden geschat door bij de actuele leeftijd van de patiënt 15 jaar op te tellen.

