# 4.3 Exclusion criteria

A potential subject who meets any of the following criteria will be excluded from participation in this study:

- None

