7.8 Drug accountability

### 8. METHODS

### 8.1 Study parameters/endpoints

### 8.1.1 Main study parameter/endpoint

To investigate, within a dental setting, the differences between subjects with and without periodontitis:

- The prevalence of preDM and DM (established cut-off values for HbA1c, appendix 1 and 2 (7))

- The 10-year-risk of ASCVD ("10-year-risk" chart, appendix 3 (20))
- The prevalence of MetS (diagnostic criteria of NCEP ATP III, appendix 4 (21))
- The risk of OSAS (OSAS risk questionnaire (22))

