### 8.1.3 Other study parameters (if applicable)

- Other study parameters that will be obtained are sex, age, ethnicity (origin of parents), education level, smoking habits, diagnosis of hypertension, diagnosis of ASCVD, medical treatment for ASCVD, relatives with ASCVD, diagnosis of hypercholesterolemia, medical treatment for hypercholesterolemia, diagnosis of rheumatoid arthritis, diagnosis of DM, relatives with DM, history of periodontal treatment, height and body weight (for determining the BMI), neck and waist circumference, blood pressure, physical activity.

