### **10.1 Primary study parameter(s)**

The cases and controls are a priori defined by inclusion and exclusion criteria. The STROBE guideline will be followed and a flow diagram will be generated of how many individuals have been screened, invited to participate, included and analysed (29). All initially included study subjects will form part of the data analysis (intention to treat). Type I error will be controlled by including a sufficient number of cases and controls to avoid multiplicities and to apply Bonferroni corrections where applicable. Secondly, we have determined the minimal sample size on the basis of an appropriate power calculation (see chapter 4.4).

The prevalence of (pre)diabetes, the 10-year risk of ASCVD, the prevalence of MetS and the prevalences of OSAS risks (categorical variables) within the study population will be compared with parametric and non-parametric tests (ANOVA and  $Chi^2$ -test). Where applicable, analyses will be corrected for multiple testing (Bonferroni). The significance level will be set to p<0.05.

The prevalence of (pre)DM among cases and controls will be firstly reported without adjustment of any of potential covariates. In a second exploratory analysis we will adjust the prevalence for general and diabetes and ASCVD related characteristics of the study population: sex, age, ethnicity (origin of parents), education level, smoking habits, relatives with DM, history of periodontal treatment, diagnosis of hypertension, diagnosis of hypercholesterolemia, diagnosis of DM and the BMI, amount of physical activity.

The 10-year risk of ASCVD will be calculated according to the algorithm from the ESC guidelines, which is adapted to the Dutch situation. No further adjustments will be done.

The prevalence MetS will be calculated according to the criteria of the NCEP ATP III guidelines. No covariates will be included.

The risk for OSAS will be assessed by the OSAS questionnaire. No further adjustments will be done. However, the results will be explored in relation to having periodontitis, the

background characteristics, the blood chemistry outcomes and having (pre)diabetes and the 10-year risk for ASCVD.

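### The 10-year ASCVD risk chart is limited to people without known ASCVD, but the plan has no rule for subjects with diagnosed ASCVD and keeps them in this main comparison

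*Combined protocol and SAP*

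**What the plan says.** Sections 2 and 8.1.1 list the 10-year ASCVD risk among four main endpoints and point to Appendix 3 for its measurement. The appendix is titled "The 10-year-risk chart of ASCVD (for patients without known ASCVD"), and the Dutch caption under the chart says the same: "10-jaarsrisico op ziekte of sterfte door HVZ voor patiënten zonder HVZ" (HVZ is cardiovascular disease).

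Eligibility does not match that limit. Section 4.2 sets no condition on ASCVD history. Section 4.3 opens with "A potential subject who meets any of the following criteria will be excluded from participation in this study" and its only entry is that there are none.

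Section 10.1 then states: "All initially included study subjects will form part of the data analysis (intention to treat"). On this endpoint it says "The 10-year risk of ASCVD will be calculated according to the algorithm from the ESC guidelines, which is adapted to the Dutch situation", and adds that nothing more will be adjusted. The opening part of section 10 fills missing data by the EM method.

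The study does record who has the disease. Section 8.1.3 lists "diagnosis of ASCVD, medical treatment for ASCVD" among the other parameters, and section 10.3 lists both as yes/no covariates. No section says how a subject with a positive answer is scored, set aside or reported for this endpoint.

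**The concern.** The chart estimates the risk of disease or death from cardiovascular disease in people who do not yet have it. For someone who already has ASCVD that quantity is not defined, so any number entered for them is not a measurement of the endpoint. The people affected are those in whom vascular disease is already established, and the study is asking whether vascular risk differs between groups. If handling is left open until the data are in hand, the choice among scoring them, imputing them, dropping them or counting them as high risk can be made with the result in view. The same gap passes to the severe versus mild/moderate comparison, because section 10.2 copies the primary procedures.

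**Working it through.** **The plan's own figure.** Section 4.4 gives 261 per group from diabetes prevalences of 8.5% and 18.1%, alpha 0.05 and 90% power. With the pooled-variance formula, two-sided and without continuity correction:

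n = [1.960 × √(2 × 0.133 × 0.867) + 1.282 × √(0.085 × 0.915 + 0.181 × 0.819)]² / 0.096² = 260.9, that is 261.

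The figure reproduces and is not in dispute. It says nothing about the ASCVD endpoint.

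**What the chart uses.** Its inputs are sex, age, smoking, systolic pressure and the total cholesterol/HDL ratio. Existing ASCVD is not an input. Readings from Appendix 3, all for non-smokers:

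- Man, 60, systolic 120, ratio 4: 8% (band below 10%).
- Man, 60, systolic 160, ratio 6: 23% (band of 20% and over).
- Woman, 50, systolic 120, ratio 4: 1% (band below 10%).

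Each reading is the same with or without diagnosed ASCVD. The chart has a special instruction for diabetes and rheumatoid arthritis, "Het risico bij patiënten met DM of RA kan worden geschat door bij de actuele leeftijd van de patiënt 15 jaar op te tellen" (add 15 years to age), but none for ASCVD.

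**What the written rules do with a subject who has diagnosed ASCVD.**

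1. Section 4.3 admits the subject.
2. Section 10.1 keeps the subject in the analysis.
3. If the chart is read, the value is outside the chart's stated population.
4. If it is not read, the value is missing, and section 10 imputes a first-event risk.

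Both routes give an invalid value.

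**Can the effect on the group difference be sized?** Let a be the proportion with diagnosed ASCVD, r the proportion at or above 20% among those without it, and s the proportion of diagnosed subjects whom the chart places at or above 20%. Then the proportion in the top band is:

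- chart read for everyone: a × s + (1 − a) × r
- restricted to no diagnosis: r
- composite (diagnosed, or chart at least 20%): a + (1 − a) × r

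The documents give none of these. Purely as assumptions, take a = 5% of controls and 10% of periodontitis subjects, and r = 15% and 20%. The restricted difference is 20 − 15 = 5.0 points. The composite difference is (0.10 + 0.90 × 0.20) − (0.05 + 0.95 × 0.15) = 28.0% − 19.25% = 8.75 points. With the chart read for everyone:

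| s | Controls | Periodontitis | Difference (points) |
|---|---|---|---|
| 0 | 14.25% | 18.0% | 3.75 |
| 0.25 | 15.5% | 20.5% | 5.0 |
| 0.5 | 16.75% | 23.0% | 6.25 |

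Against the restricted analysis, reading the chart for everyone can shrink, leave unchanged or enlarge the difference. With a from 3%/6% to 8%/15% and s from 0 to 0.5, the chart difference runs from 3.2 to 6.7 points around the same 5.0.

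**The case against.** The best reply is that the plan is silent on this, which is different from planning an error. The endpoint is defined by reference to an appendix whose title carries the restriction, and no section orders the chart to be read for people with ASCVD. They could stay in the study and simply have no chart value. Section 10.1 also cites a guideline-derived algorithm that might treat them separately. The diagnosis is collected, so restriction would be possible at analysis.

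Part of this stands: the plan does not affirmatively direct an out-of-domain reading. But leaving these subjects out conflicts with the statement that all are analysed, and leaving their value blank brings in EM imputation. The documents do not say that the algorithm handles known ASCVD. Listing the diagnosis as a covariate does not help, because a covariate cannot repair an outcome that is undefined for the subject.

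Three stronger readings are tempting, and the documents do not support them.

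- **Bias towards no difference.** A reader might infer that diagnosed ASCVD is commoner with periodontitis and that low scores for these subjects hide part of the difference. The hypothesis in section 1 concerns raised 10-year risk, not the frequency of diagnosed disease. The shrinkage is also assured only against the composite, which the protocol does not name as its endpoint.
- **A size in percentage points.** Assume 10% versus 4% diagnosed, with half reading below 20%. Against the composite, the difference shrinks by (0.10 − 0.04) × 0.5 = 3 points. Against restriction, with r = 20% and 15%, it grows by 0.10 × (0.5 − 0.20) − 0.04 × (0.5 − 0.15) = 1.6 points. The sign depends on the comparator and on assumed rates.
- **Ages off the chart as an equal defect.** Rows run from 40 to 70, inclusion starts at 18, and the 15 years for diabetes or rheumatoid arthritis take anyone over 55 past the last labelled age. In the chart's three bands this matters little: 78 of 80 cells in the 70 row are 20% or over, and 78 of 80 in the 40 row are below 10%. Assigning such subjects to the end rows would itself be reading outside the chart.

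**Conclusion.** The concern holds as a conflict within the text. A main endpoint is taken from an instrument limited to people without known ASCVD, while the eligibility, analysis-set and imputation rules together carry people with diagnosed ASCVD into the comparison with a value that is not valid for them. This follows from the documents alone and rests on no assumption about rates, except that some enrolled subjects will have diagnosed ASCVD, which the protocol foresees by recording it.

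The effect on the group difference is undetermined in both size and direction, because the documents give neither the prevalence of diagnosed ASCVD nor how such subjects would read on the chart. The percentages in the table illustrate that indeterminacy; they are not estimates. The sample size of 261 per group is unaffected. The rule should be fixed before the data are analysed.

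**What to change.** In section 10.1:

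- Restrict the 10-year-risk comparison to subjects with no recorded diagnosis of ASCVD, and state this as an exception to the rule that all included subjects are analysed.
- State that chart risk is not imputed by EM for subjects with diagnosed ASCVD.
- Report the number and prevalence of diagnosed ASCVD in each group beside the comparison, so that the excluded disease stays visible.
- Add one sensitivity analysis of a composite: diagnosed ASCVD, or chart risk of at least 20%.

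Apply the same rules to severe versus mild/moderate periodontitis in section 10.2. Optionally, note the chart's age span and add a sensitivity analysis limited to effective ages (after any added 15 years) of 40 to 70.

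The change is to wording only, since the diagnosis is already collected and no new exclusion from the study is needed. The cost is a smaller n for this one endpoint. Under the assumed 5% and 10%, about 261 × 0.05 + 522 × 0.10 = 65 of 783 subjects leave the comparison; across the wider assumed range (3%/6% to 8%/15%) it is about 39 to 99. Restriction makes the endpoint valid but should not be expected to raise power: with the same assumed rates and s = 0.25, power is 0.37 restricted, 0.39 with the chart read for everyone, and 0.77 for the composite.

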# APPENDIX 4: Criteria for diagnosis of Metabolic Syndrome (MetS) according to the NCEP ATP III (21)

Measure (any 3 of 5 constitute	Categorical cutpoints
diagnosis of metabolic syndrome)	
Elevated waist circumference (WC)	$\geq$ 102 cm in men
	$\geq$ 88 cm in women
Elevated triglycerides (TG)	$\geq$ 1.7 mmol/L
	or
	On drug treatment for elevated TG
Reduced HDL-C	< 1.03 mmol/L in men
	< 1.3 mmol/L in women
	or
	On drug treatment for reduced HDL-C
Elevated blood pressure	≥ 130 mmHg systolic blood pressure
	or
	≥ 85 mmHg diastolic blood pressure
	or
	On antihypertensive drug treatment in a
	patient with a history of hypertension
Elevated fasting glucose	$\geq$ 5.6 mmol/L

# APPENDIX 5 Case Definitions Periodontitis according to the CDC-AAP (23)

Case	Definition †					
No periodontitis	No evidence of mild, moderate, or severe periodontitis					
Mild periodontitis	≥2 interproximal sites with AL ≥3 mm, and ≥2 interproximal sites with PD ≥4 mm (not on same tooth) or one site with PD ≥5 mm					
Moderate periodontitis	≥2 interproximal sites with AL ≥4 mm (not on same tooth), or ≥2 interproximal sites with PD ≥5 mm (not on same tooth)					
Severe periodontitis	≥2 interproximal sites with AL ≥6 mm (not on same tooth) and ≥1 interproximal site with PD ≥5 mm					

 
* These definitions are now commonly referred to as the CDC-AAP case definitions for surveillance of periodontitis.
 
† Third molars excluded; total periodontitis is defined as the sum of mild, moderate, and severe disease.
 

